Cognitive Reappraisal Intervention for Suicide Prevention (CRISP): An Intervention for Middle-Aged and Older Adults Hospitalized for Suicidal Ideation or Suicide Attempt

Weill Cornell Medicine; NCT 03026127

Operations Manual
June 2020

Sponsored by the National Institutes of Health (NIH)

BACKGROUND

Suicide rates in middle-aged and older adults are alarmingly high, and suicide risk increases for those who have been hospitalized for suicidal ideation or suicide attempt. Reducing suicide rates in at-risk populations is a major NIMH priority. To address this need, we developed Cognitive Reappraisal Intervention for Suicide Prevention (CRISP) to help middle-aged and older adults (50 years old and older) reduce their suicide risk after a suicide- related hospitalization.

CRISP draws on recent advances in affective neuroscience and aims to improve cognitive reappraisal ability (i.e. the ability to modify the appraisal of a situation to alter its emotional significance) and reduce suicide risk. Our conceptual framework is based on the premises that: a) suicidal ideation and behavior are associated with unsuccessful attempts to regulate intense negative emotions, including depression, anxiety, hopelessness, irritability, anger, and guilt; b) cognitive reappraisal is an effective emotion regulation strategy with identified and investigated neurobiological correlates; c) decreased cognitive reappraisal is associated with increased suicide risk; and d) cognitive reappraisal strategies can be effectively used to reduce suicide risk in our population. We place emphasis on suicidal ideation, in addition to suicidal behavior, because suicidal ideation after a suicide-related hospitalization is a known significant risk factor for suicide. CRISP also employs environmental adaptations/aids to assist patients in utilizing CRISP techniques between sessions (WellPATH personalized tablet app, written step-by-step plan, phone calls). We focus on the first 3 months post-discharge from a suicide-related hospitalization, a period of high suicide risk.

Behavioral interventions for middle-aged and older adults with depression and suicidal ideation are scarce. This project aims to meet the needs of middle-aged and older adults who have been discharged after a hospitalization for suicidal ideation or suicide attempt with any depression or anxiety disorder. We exclude bipolar patients in mixed, hypomanic, or manic state, and patients with psychosis or dementia. Regulation of emotions associated with mixed, hypomanic and manic state may need different techniques than those covered in CRISP.

Consistent with the NIMH *Strategy 3.1*, CRISP is a novel intervention on a mechanism of action, cognitive reappraisal, to reduce suicide risk. In response to NIMH *Strategy 4.3*, The WellPATH app is an innovative tablet application with personalized cognitive reappraisal techniques to improve cognitive reappraisal and potentially reduce suicide risk. Finally, CRISP's use of cognitive reappraisal, application to cross-diagnostic categories and use of two different levels of analysis are consistent with NIMH's RDOC initiative.

Middle-aged and older adults, who have been hospitalized for suicidal ideation or suicide attempt, are an at-risk and understudied population. If effective, CRISP may

decrease suicide risk, reduce depression, and improve quality of life for this vulnerable group.

STUDY AIMS

The goals of the study are:

MONTHS 1-3:

1. Finalize the CRISP Manual and establish feasibility of therapist training. We will train 4 LMSW/LCSWs: 2 will be trained in the CRISP therapy, 2 will be trained in Supportive Psychotherapy. We will determine the success rate of training and number of hours needed to achieve CRISP certification.

MONTHS 4-24:

[figure not shown]
2. Assess CRISP's reach, feasibility and acceptability: We will assess across conditions:
 - a. Reach: Number of patients screened, and those who meet inclusion criteria;
 - b. Feasibility: Number of patients who receive CRISP or ST for mental health care and research procedures (timely referrals, assessments);
 - c. Acceptability: Patient's treatment satisfaction at 6, 12, and 24 weeks.

Benchmarks of the study progress: Feasibility: At least 75% of CRISP participants will complete CRISP. Acceptability: We will obtain treatment satisfaction scores at the end of CRISP treatment.

[figure not shown]
3. Preliminary Effectiveness: Over the course of 12 weeks, CRISP participants, compared to participants receiving Supportive Psychotherapy will show an improvement in cognitive reappraisal and have greater (effect size) and clinically significant reductions in suicidal risk.

OVERVIEW OF DESIGN

Figure 1.

RESEARCH ASSESSMENTS

Inclusion Criteria:

1. Age equal to or more than 50 years and up to age 90.
2. Any DSM-5 depression or anxiety diagnosis, including major depressive disorder, bipolar depression, depressive disorder Not Elsewhere Classified, anxiety disorder Not Elsewhere Classified, adjustment disorder with anxiety and depressed mood.
3. Hospitalized for suicidal ideation (either active or passive) or suicide attempt; at hospital admission, Columbia Suicide Severity Rating Scale should greater or equal to 3.
4. Mini Mental State Exam more than or equal to 24.
5. English speaking.
6. Capacity to consent.

Exclusion Criteria:

1. Not having Major Depressive Disorder (by SCID, DSM-IV.)
2. Primary Psychotic Disorder.
3. Currently Hypomanic, Manic or Mixed Episode.
4. Diagnosis of Dementia.
5. Active SI to the point they present as a danger to themselves or others.
 - a. *Alert [name] & complete Suicide Risk Assessment.
6. Acute or Severe Medical Illness (i.e., delirium; decompensated cardiac, liver or kidney failure; major surgery; stroke or myocardial infarction during the three months prior to entry).
7. Aphasia, sensory problems and/or inability to speak English.

*Note: Patients on psychotropic medications, opioids or benzodiazepines will be included if they do not meet DSM-5 criteria for opioid, anxiolytics or other substance abuse disorders (Human Subjects).

INTERVENTION

CRISP:

CRISP utilizes a structured, yet personalized, approach. The goals of CRISP are to use cognitive reappraisal techniques to reduce negative emotions associated with self-harm and to increase involvement in meaningful and pleasurable activities. The CRISP therapist uses the following techniques: identification and evaluation of negative emotions and their relationship with patient's difficulties, suicidal ideation and suicidal behavior (e.g. explore utility of negative emotions and change perspective about trigger) and use of a range of emotion regulation techniques (e.g. situation selection, situation modification, attentional deployment, cognitive reappraisal and response modulation). Environmental aids, including a personalized tablet application are used to augment the CRISP intervention. Finally, at the end of treatment CRISP therapists provide to patients a personalized summary of treatment that highlights the problems that were addressed, and the successful techniques that had been used to solve them.

Comparison Condition: Supportive Therapy:

ST is a control intervention not aimed to improve emotion regulation, including cognitive reappraisal. The ST therapist strives to create a positive alliance with the patient by emphasizing non-specific therapeutic interactions and techniques that convey to the patient, interest, concern and understanding. For the purposes of this study, an effort will be made to avoid all emotion regulation techniques that relate to Cognitive Reappraisal Intervention for Suicide Prevention (CRISP).

FOLLOW-UP ASSESSMENTS

Follow-up assessments are conducted by the WCM research assistant at 6, 12, and 24 weeks after the baseline and include measures of depression and anxiety symptoms, medical burden, and suicidal ideation. Subjects will receive \$50 (cash, check, or gift card) as compensation for completing each assessment. They may also be eligible for up to an additional \$10 for one of the EEG computer tasks.

PROCEDURES FOR TREATMENT AFTER STUDY COMPLETION

Participants whose follow-up assessments indicate a need for continued mental health services will be provided with mental health referrals.

DATA MANAGEMENT

Data will be collected by the study RA at baseline and at follow-up assessments. The RA will also be responsible for writing and presenting patient summaries to the PI. The therapist will complete updates on the progress of their therapy sessions. [name] manages the CRISP database and weekly reporting.

Research records will be kept confidential to the extent permitted by law. Subjects will be assigned ID numbers by the CRISP study team, and all identifying information will be removed from records that are submitted to Weill Cornell Medicine for data analysis. Paper research records will be kept in locked file cabinets. When necessary for purposes of auditing, the Cornell IRB, NIMH, and all Federal oversight agencies will be provided access to these files. Computers will be password-protected, and all staff participating in the study will be trained in protecting human subjects in research. Data will be published in aggregate form without unique identifiers. No analyses will be published in which it is possible to identify individuals based on data.

[REDACTED]

[REDACTED]

[REDACTED]

[REDACTED]

[REDACTED]

[REDACTED]

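### Does the Background's broader psychosis exclusion contradict exclusion item 2 in a way that needs a change?

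*Protocol*

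**What the plan says.** The Protocol describes who is kept out of the study in two places.

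- Background, in a short narrative on the target population: "We exclude bipolar patients in mixed, hypomanic, or manic state, and patients with psychosis or dementia". The word for psychosis carries no qualifier.
- Research Assessments, Exclusion Criteria, a list of seven numbered items. Item 2 is the only one on psychosis: "Primary Psychotic Disorder". Item 3 covers mood state, "Currently Hypomanic, Manic or Mixed Episode", and item 4 covers dementia, "Diagnosis of Dementia".

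Two further items bear on the case. Inclusion item 2 is broad: "Any DSM-5 depression or anxiety diagnosis, including major depressive disorder, bipolar depression". It says nothing for or against psychotic features. Exclusion item 1 removes patients on the ground "Not having Major Depressive Disorder (by SCID, DSM-IV". No part of the text shown defines psychosis, mentions a mood disorder with psychotic features, or says which section prevails if the two differ.

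**The concern.** Taken literally, the two terms cover different groups. Someone whose depressive episode has psychotic features has psychosis, but the main diagnosis is a mood disorder and not a primary psychotic one. The Background seems to bar that person, while the list seems to let the person through.

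The study recruits people hospitalized for suicidal ideation or a suicide attempt who have depression or anxiety, so it is plausible that a screener would meet such a case. The document is also titled an operations manual, so staff may work directly from it. Two screeners relying on different sentences could decide differently. A report that described the sample in the Background's words could then be inaccurate about who was enrolled.

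**Working it through.** No figure in the Protocol depends on this point, so there is nothing to recompute. The check is a side-by-side reading.

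**Step 1: follow one patient through the criteria.** The test case is a patient with major depressive disorder with psychotic features.

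| Provision | Effect on this patient |
|---|---|
| Background sentence | Excluded, if psychosis is read without limit |
| Inclusion 2 | Met, since the patient has a depressive diagnosis |
| Exclusion 1 | Not triggered, since the patient has major depressive disorder |
| Exclusion 2 | Not triggered, if a mood disorder with psychotic features is not counted as primary psychotic |
| Exclusions 3 and 4 | Not triggered by this diagnosis |
| Exclusion 5, "Active SI to the point they present as a danger to themselves or others" | Depends on current risk, not on psychosis |
| Exclusion 6, "Acute or Severe Medical Illness (i.e., delirium; decompensated cardiac, liver or kidney failure; major surgery; stroke or myocardial infarction" | Medical; the only mental-state example is delirium |
| Exclusion 7 | Concerns aphasia, sensory problems and language |
| Inclusion 6 (capacity) | May remove an individual, but is not a psychosis rule |

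So 0 of 7 numbered exclusions remove this patient because of psychosis. The mismatch in scope is confirmed.

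**Step 2: ask whether the two places contradict each other.** A contradiction needs one place to admit what the other bars. The list is silent on psychotic depression, and admission is only inferred from a broad inclusion item and that silence. A screener who applies the Background and the list together excludes the patient and breaks neither. This is an ambiguity of scope.

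**Step 3: ask whether the Background sentence is exact elsewhere.** It is not.

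- Mood state: the Background ties this to bipolar patients; item 3 has no such limit.
- Dementia: the Background names the condition; item 4 asks for a diagnosis.
- Psychosis: the Background names the condition; item 2 names a diagnostic class.

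All 3 elements are reworded. The natural reading is a one-sentence paraphrase of items 2 to 4, with the numbered list as the working rule.

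**Step 4: trace the consequences through the stated aims.**

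- Reach counts patients screened and those meeting the inclusion criteria. Read literally, an exclusion item does not alter that count.
- The feasibility benchmark, at least 75% of CRISP participants completing, is a proportion of those enrolled in that arm. It can be calculated under either reading.
- Acceptability is collected from whoever is treated.
- Preliminary effectiveness compares CRISP with supportive therapy over 12 weeks. If eligibility is decided before assignment, a wider or narrower psychosis rule changes who is in both groups and does not favour one of them.

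**The case for a change.** The strongest case for acting is that the Background sentence is worded as a rule, that its mood-state and dementia elements have recognisable counterparts in the list, and that only psychosis clearly shrinks on the way. Even if the list governs, the Background then describes the population too narrowly. The point also survives whichever way the separate tension between inclusion 2 and exclusion 1 is resolved: under the wider diagnostic rule, bipolar depression with psychotic features becomes a second undecided case.

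Part of this stands. The terms do differ, the text shown does not decide the case, and using one term in both places would be tidier. Two steps do not hold. First, the claim of opposite answers goes too far, because the list gives no answer in favour of admission. Second, the importance is asserted without support: the Protocol gives no share of screened or enrolled patients with psychotic features, and no effect on the treatment comparison can be shown. Figure 1 and the human-subjects material that the eligibility note points to are also not available here, so a clarification may exist that cannot be seen.

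**Conclusion.** This is a minor wording inconsistency between a narrative summary and an operative list, and no change to the plan follows from it. It affects one term. The gap is one that study staff and authors can fill sensibly: screen by the numbered criteria, or by both places together, and describe the enrolled sample by the criteria actually applied. Either course leaves a definable population and an interpretable comparison in a study whose aims are feasibility, reach, acceptability and preliminary effectiveness.

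The conclusion rests on three assumptions. The numbered criteria are taken as the working rule, which is the usual reading although the Protocol does not say so. Eligibility is taken to be settled before treatment is assigned; the text shown does not describe the assignment step. The number of patients with psychotic features is unknown. A large number would make it more important to describe the sample carefully, but would not bias the comparison under the second assumption. Whether such patients ought to be in or out is a clinical choice for the sponsor, and this review takes no position on it.

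### Does training two separate therapists for each therapy spoil the preliminary comparison in Aim 3?

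*Protocol*

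**What the plan says.** In the protocol's STUDY AIMS section, Aim 1 covers months 1 to 3 and concerns the CRISP manual and the feasibility of training. It says "We will train 4 LMSW/LCSWs" and divides them: "2 will be trained in the CRISP therapy, 2 will be trained in Supportive Psychotherapy". Its measures are the success rate of training and the "number of hours needed to achieve CRISP certification".

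Aim 3, headed as preliminary effectiveness, sets out the comparison: "Over the course of 12 weeks, CRISP participants, compared to participants receiving Supportive Psychotherapy" are expected to improve in cognitive reappraisal and to "have greater (effect size) and clinically significant reductions in suicidal risk".

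The INTERVENTION section describes the two therapist roles separately. For CRISP it begins "The CRISP therapist uses the following techniques". The supportive therapist is to keep away from emotion regulation techniques related to CRISP.

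The text shown does not say whether other therapists treat patients, how the four were divided, or how patients are matched to a therapist. The design figure and the blocks at the end are not visible.

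**The concern.** When each therapist works in one condition only, therapist and therapy cannot be told apart. With two people per condition, a strong or weak pair shifts the whole arm. This could matter in two ways.

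- **Precision.** Patients of one therapist tend to have similar outcomes. An interval that treats all patients as independent would then be too narrow, and with four therapists only 4 − 2 = 2 degrees of freedom remain at therapist level.
- **Direction.** If the abler therapists went to CRISP, the estimate would lean towards CRISP, and no later analysis could remove this. The team has an interest in the result: the BACKGROUND says "we developed Cognitive Reappraisal Intervention for Suicide Prevention (CRISP", and the same team trains both pairs. CRISP is also the only therapy for which Aim 1 names a certification.

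At stake is how far the Aim 3 effect size can be read as an effect of the therapy itself.

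**Working it through.** **Inputs.** From Aim 1: k = 2 therapists per condition, none shared. The text shown gives no sample size, SD, caseload, ICC, significance level or interval method, so there is no stated figure to reproduce. Assumed for illustration: outcome SD = 1, N = 30 patients per arm (range 20 to 40), equal caseloads m = N/2, and ICC from 0 to 0.10.

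**Step 1: what the contrast contains.** Arm difference = therapy effect + (mean effect of the CRISP pair − mean effect of the supportive pair). With no shared therapist, the data give only the sum. This holds if only these four treat patients.

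**Step 2: precision if the split is neutral.** SE = √[(2/k)(ICC + (1 − ICC)/m)]. For k = 2 and m = 15 and ICC 0.05: √(0.05 + 0.95/15) = 0.337. Ignoring therapists: √(2/30) = 0.258, with half-width 1.96 × 0.258 = 0.506. Coverage of that patient-level interval = 1 − 2[1 − Φ(0.506/SE)].

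| ICC | SE | SE ÷ 0.258 | Coverage of nominal 95% interval |
|---|---|---|---|
| 0 | 0.258 | 1.00 | 95% |
| 0.01 | 0.276 | 1.07 | 93.4% |
| 0.02 | 0.292 | 1.13 | 91.7% |
| 0.05 | 0.337 | 1.30 | 86.7% |
| 0.10 | 0.400 | 1.55 | 79.4% |

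For N of 20 to 40 per arm and ICC 0.01 to 0.10, the SE ratio runs from 1.04 to 1.70 and coverage from 94.0% down to 75.0%.

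**Step 3: the 2-df interval.** At ICC 0.05 the therapist-level half-width is 4.303 × 0.337 = 1.45 SD, against 0.51 SD at patient level. Most of the gap comes from the t multiplier: 4.303 × 0.258 = 1.11 SD even at ICC 0. The larger SE with the usual multiplier gives only 1.96 × 0.337 = 0.66 SD.

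**Step 4: bias if the split follows skill.** Among four standard normal values, the two largest have expected values 1.029 and 0.297, with mean 0.663. By symmetry the top pair exceeds the bottom pair by 2 × 0.663 = 1.326. If the CRISP pair is the top two on a trait correlated r with effectiveness, bias = r × 1.326 × √ICC. For r = 0.5 and ICC 0.01, 0.02, 0.05 and 0.10 this is 0.07, 0.09, 0.15 and 0.21 SD. Under a random draw it is 0. The largest of these is 0.210/0.258 = 0.81 of one patient-level SE.

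In simulation with no true difference, N = 30 and ICC 0.05, a patient-level 95% interval lies wholly in CRISP's favour in 6.7% of trials under a random split and in 13.7% with r = 0.5. The nominal rate is 2.5%.

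**Step 5: what these results attach to.** Steps 2 and 3 describe an interval that ignores therapist, and the text shown states no such interval. Step 4 needs placement by skill, which the text shown does not mention. Only Step 1 follows from the protocol, and it depends on the four being the only therapists.

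**The case for a change.** The best case for a change is this. The training months lead straight into the patient phase (months 4 to 24) and no other therapists are named, so the natural reading is that these four treat everyone. Who is trained in what is a design decision and not an analysis detail, so an analysis plan cannot repair a split that favoured one side. Calling the aim preliminary does not tell a reader that the result may partly reflect which two people delivered each therapy. A sentence of disclosure would cost almost nothing.

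Much of this stands. The reading is likely, the confounding follows from it, and with 2 degrees of freedom no model fully restores precision.

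Three things weaken it as a reason to change the plan.

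- The features that Aim 1 fixes, four therapists and no sharing, are reasonable for a small study whose control therapy must stay free of CRISP techniques. Sharing therapists would risk the contamination that separation helps to avoid.
- The evidence for a non-neutral split is thin. Developers commonly train the therapists in a first study, and naming CRISP certification is what a training-feasibility aim for CRISP would do. Neither fact shows placement by skill.
- A random draw is open only before training starts, which the June 2020 manual does not settle. It would leave the chance difference between pairs untouched. It would also give up placement by interest or skill, which could affect certification with only two CRISP trainees.

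**Conclusion.** No change to the plan follows. The structural point is true: if only these four therapists treat patients, the Aim 3 effect size is that of each therapy as delivered by its pair. Under the assumed 20 to 40 patients per arm and ICC of 0.01 to 0.10, the true SE would be 1.04 to 1.70 times the patient-level SE; at an ICC of 0 nothing is lost. These figures rest on assumed numbers and on an analysis that the protocol does not state. The bias of 0.07 to 0.21 SD further assumes a skill-related split with no support in the text.

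What remains is a fair trade-off between contamination and therapist confounding, in an aim already called preliminary. Two details are not stated: who treats, and how the four were divided. The missing figure or redacted blocks may give them. Analysts can take the therapist structure into account and describe the estimate accordingly without any amendment to the protocol.

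### Does an acceptability benchmark that no satisfaction score can fail need to be rewritten?

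*Protocol*

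**What the plan says.** Aim 2 in the Protocol's Study Aims (months 4 to 24) covers three domains in both arms: "reach, feasibility and acceptability: We will assess across conditions".

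- Reach (Aim 2a) is a count: "Reach: Number of patients screened, and those who meet inclusion criteria".
- Acceptability (Aim 2c) is defined by a measure and its time points: "Acceptability: Patient's treatment satisfaction at 6, 12, and 24 weeks".
- A paragraph of study-progress benchmarks follows. For feasibility: "At least 75% of CRISP participants will complete CRISP". For acceptability: "We will obtain treatment satisfaction scores at the end of CRISP treatment". Reach has no entry there.

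The Follow-up Assessments section gives the same three time points: "Follow-up assessments are conducted by the WCM research assistant at 6, 12, and 24 weeks after the baseline". Its list of content names symptom measures, medical burden and suicidal ideation, and does not mention satisfaction. The text shown names no satisfaction instrument, scale range, cut-off, target proportion or sample size.

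**The concern.** A benchmark is normally something that results can miss. The feasibility entry works that way, since completion below 75% fails it. The acceptability entry beside it does not, because it is met by the act of collecting scores, whatever they show.

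Assessing CRISP's acceptability is a stated aim, so the label matters. If a later report said that the acceptability benchmark was met, the statement would be true even if patients had disliked the treatment. A reader could take it as support for CRISP, particularly next to a completion benchmark that was really at risk. The natural suggestion is to replace the sentence with a minimum satisfaction level fixed before any scores are seen.

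**Working it through.** There is no stated figure to reproduce and no arithmetic that bears on the point. The protocol gives no sample size, satisfaction scale or threshold. Any probability of passing a satisfaction mark would describe a rule supplied from outside, not this plan. The check is therefore one of reading and logic.

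1. **Can a satisfaction result fail the entry?** The entry's only condition is that end-of-treatment scores are obtained. Given that they are, it is met whether every score is at the bottom or the top of the scale. It fails only through non-collection, and no minimum completeness is stated. The observation behind the concern is correct.

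2. **What kind of statement is it?** The paragraph heading refers to the progress of the study, not to criteria for the success of CRISP. Under such a heading one entry can be a performance target (75% completion) and another a collection milestone. The word acceptability at the front of the second entry makes the label ambiguous, but the sentence after it says plainly what will be done.

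3. **Is acceptability assessed elsewhere?** Yes. Aim 2c defines it as "treatment satisfaction at 6, 12, and 24 weeks", and the lead-in to Aim 2 applies this to both conditions. That gives satisfaction by arm at three time points, which tells a reader more about acceptability than a single pass or fail.

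4. **Does anything depend on the benchmark?** The text shown has no stopping rule, continuation decision or analysis that refers to it. Aim 3, the preliminary comparison on cognitive reappraisal and suicide risk, is defined without it.

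5. **What would a rewrite change?** A pass mark needs an instrument, a cut-off and a proportion. None can be derived from the protocol, and all are details commonly held in a statistical analysis plan. Relabelling the sentence as a data-collection milestone would be accurate, but it would change no data, estimate or comparison.

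**The case for a change.** The strongest opposing case is that this is not a missing detail. The protocol chose to state a benchmark, called it acceptability, and gave it content that does not measure acceptability. A statistical analysis plan could add a criterion, yet the sentence would still stand. The feasibility entry shows that the authors knew how to write a benchmark that can be missed, and the correction would cost little.

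A second strand concerns who is scored. Scores taken when CRISP treatment ends might come from completers only. At exactly 75% completion, the proportion satisfied among completers exceeds the proportion among all assigned by (1 − 0.75) × (completers' proportion − stoppers' proportion), which is at most 0.25 × (1 − 0) = 25 percentage points.

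The first strand stands as a remark on wording: the entry should not be cited as evidence that patients accepted the treatment. It does not show that the plan produces a wrong or missing result, because acceptability is described under Aim 2c whatever the benchmark is called.

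The second strand does not touch the plan. The protocol states neither a satisfaction proportion nor a completers-only denominator. The 25-point bound also needs every completer satisfied and every stopper dissatisfied. It is a caution for anyone who later sets a satisfaction mark.

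One limit remains. A figure that is not reproduced follows the benchmark paragraph. Nothing in the text points to it for a threshold, but its content cannot be checked.

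**Conclusion.** No change is needed. The acceptability entry is in substance a data-collection milestone under a study-progress heading, and no satisfaction value can fail it. That is a loose label with no effect on any planned decision, on the Aim 2c description of satisfaction, or on the effectiveness comparison. Describing satisfaction without a pass mark is a fair choice for a study that calls its own effectiveness aim preliminary.

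This rests on two assumptions: that satisfaction is in fact collected in both arms at 6, 12 and 24 weeks as Aim 2c says, although the follow-up content list does not name it; and that statements about acceptability are based on those scores. An analyst writing the report would ordinarily present satisfaction by arm and time point, with the number responding, and would not offer the obtaining of scores as a finding about CRISP.

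### Exclusion criterion 1 requires major depressive disorder, which cancels most of inclusion criterion 2 and contradicts the stated target population

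*Protocol*

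**What the plan says.** The eligibility criteria stand under Research Assessments in the Protocol.

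- **Inclusion criterion 2** admits "Any DSM-5 depression or anxiety diagnosis, including major depressive disorder, bipolar depression, depressive disorder Not Elsewhere Classified", and the list continues with "anxiety disorder Not Elsewhere Classified, adjustment disorder with anxiety and depressed mood".
- **Exclusion criterion 1** removes anyone "Not having Major Depressive Disorder (by SCID, DSM-IV)".
- **The Note under the exclusion list** says that patients on certain medications "will be included if they do not meet DSM-5 criteria for opioid, anxiolytics or other substance abuse disorders".

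The Background gives the target population as patients "discharged after a hospitalization for suicidal ideation or suicide attempt with any depression or anxiety disorder". Its own summary of exclusions covers bipolar patients in a mixed, hypomanic or manic state, psychosis and dementia. Absence of MDD is not mentioned. The Background also presents "application to cross-diagnostic categories" as part of the rationale.

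**The concern.** A patient enters a trial by meeting every inclusion criterion and no exclusion criterion. Read that way, exclusion 1 turns a broad diagnostic entry rule into an MDD-only rule. The Background and inclusion 2 describe a different, wider trial.

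Three things are at stake:

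- **Who is enrolled.** Two screeners could reach opposite decisions on the same patient, for example one with an anxiety disorder and no MDD, and each could cite this document.
- **Whom the results describe.** An MDD-only sample would not support statements about any depressive or anxiety disorder, and would fit poorly with a cross-diagnostic rationale. If exclusion 1 is set aside in practice, each participant without MDD is a protocol deviation.
- **The reach measure.** Study Aim 2a counts patients screened and those meeting the inclusion criteria. Taken literally, a patient without MDD can count toward reach and still be barred from entry.

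**Working it through.** The Protocol gives no figure to reproduce here. The check is logical: take each diagnosis named in inclusion 2 and ask whether it qualifies a patient on its own once exclusion 1 applies.

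| Diagnosis named in inclusion 2 | Admitted by inclusion 2 | Survives exclusion 1 on its own |
|---|---|---|
| Major depressive disorder | Yes | Yes |
| Bipolar depression (listed separately from MDD) | Yes | No |
| Depressive disorder, not elsewhere classified | Yes | No |
| Anxiety disorder, not elsewhere classified | Yes | No |
| Adjustment disorder, anxious and depressed | Yes | No |

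Five diagnoses are named, one survives, and 5 − 1 = 4 do not. This counts labels in an open list, not patients. A patient with MDD and a comorbid anxiety disorder stays eligible.

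**Can the rest of the text reconcile the two criteria?**

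- Exclusion 1 is not limited to any subgroup.
- Exclusion 3 screens out current hypomanic, manic or mixed episodes, and the Background does the same for bipolar patients. Both make sense chiefly if other bipolar patients can enter, yet exclusion 1 removes bipolar depression without MDD.
- The Background's list of exclusions omits absence of MDD.

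So the visible text contains no reconciling statement, and exclusion 1 conflicts with several other statements.

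**DSM edition.** Inclusion 2 and the Note refer to DSM-5. Exclusion 1 alone refers to DSM-IV. If an MDD requirement is kept, the document does not say which edition's diagnosis governs entry.

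**Possible effect on recruitment.** The document gives no case mix, so this is illustration only. Let p be the assumed share of otherwise eligible patients without MDD. Exclusion 1 then leaves 100(1 − p) per 100, and the same enrolment needs 1/(1 − p) times as many otherwise eligible patients.

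| Assumed p | Left per 100 | Multiplier 1/(1 − p) |
|---|---|---|
| 0.10 | 90 | 1.11 |
| 0.25 | 75 | 1.33 |
| 0.40 | 60 | 1.67 |

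The finding does not depend on these values.

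**The case against.** The best reply is that the intent is fairly clear. Exclusion 1 stands alone against the stated population, the Background's account of its exclusions, the cross-diagnostic rationale, the five named diagnoses and exclusion 3. It may be text left over from another study. This is a good argument for deleting the line, but it does not remove the conflict. Nothing in the document marks the line as an error, a written exclusion binds until it is amended, and probable intent does not tell a reader what screeners did.

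Four further points deserve weight:

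- **Internal validity.** The criterion acts before entry and alike in both conditions, so it does not bias the comparison of CRISP with supportive therapy. That stands. The harm is to eligibility, generalisability and compliance.
- **Unseen text.** The design figure is not shown, some closing text is redacted, and the Note points to a human-subjects section that is not part of this document. Fuller eligibility wording may exist elsewhere. This limits any inference about actual practice, but not the finding that these criteria conflict as written.
- **DSM edition.** The mismatch is secondary. The Note concerns substance use disorders, no patient is shown whose eligibility turns on the edition, and deleting exclusion 1 would remove the mismatch.
- **Assumed shares.** Nothing in the document anchors the 10% to 40% range, and it carries no weight in the conclusion.

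**Conclusion.** The concern holds: the eligibility rule is wrong as written. Applied jointly, inclusion 2 and exclusion 1 admit only patients with MDD, so four of the five named diagnoses lose their effect as qualifying diagnoses. That contradicts the population stated in the Background. The conclusion rests only on the ordinary reading that a participant must meet all inclusion criteria and no exclusion criterion. How many patients are affected cannot be determined from the document. Because the conflict decides who may enter and which population the results describe, it must be fixed.

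**What to change.** Reconcile the passages by amendment so that one population is defined under one DSM edition. There are two routes:

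1. **Delete exclusion 1.** This agrees best with inclusion 2, exclusion 3 and the Background. It costs one deleted line and also removes the DSM-IV reference.
2. **If an MDD-only trial is intended,** rewrite inclusion 2 as MDD and narrow the Background's statements on the target population and on cross-diagnostic application. Exclusion 3 and the Background's sentences on bipolar patients should be checked at the same time, since they presuppose that some bipolar patients can enter. This takes several edits and keeps the smaller recruitment pool.

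Under either route, name the same DSM edition in inclusion 2, in the Note and in any MDD criterion that is kept. State whether the reach count in Study Aim 2a uses the inclusion criteria alone or full eligibility. Neither route adds study procedures.

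If any screening has taken place, report which rule was applied, how many patients were rejected under exclusion 1 alone, and how many participants without MDD were enrolled.
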